Cladribine (2-chloro-2'-deoxyadenosine [2-CdA]) is a synthetic anti-neoplastic drug that belongs to the subgroup of agents called purine analogs. Cladribine Tablets have been approved by the EMA in 2017 for the treatment of adult MS patient with high active disease (see Section 2).

CLARITY Clinical Trial (NCT00213135)

In the Phase III, multi-center, randomized, double-blind CLARITY clinical trial (NCT00213135), treatment with Cladribine Tablets demonstrated a significant reduction in the annualized relapse rate (ARR) at 2 years from 0.33 to 0.14 when compared with placebo. This corresponded to an ARR risk reduction of 57.4% for the 3.5 mg/kg dose. The reduction in ARR was also consistent across various patient subgroups, including those with highly active disease. Furthermore, the CLARITY study demonstrated that Cladribine Tablets were significantly superior to placebo in the treatment of RRMS across all clinical and MRI efficacy outcomes (Giovannoni, 2010).

The CLARITY-EXT study showed that in patients who followed Cladribine Tablets with placebo, a substantial proportion remained free from indicators of disease activity, regardless of prior active treatment in CLARITY. Overall rates of (clinical and MRI) disease activity-free status were consistently high, although a longer treatment gap resulted in lower proportions of patients with no new T1 Gd+ lesions compared with those who had a shorter treatment gap (Comi, 2018).

ORACLE MS Clinical Trial (NCT00725985)

The ORACLE MS clinical trial (NCT00725985) was a Phase III, randomized, double-blind, placebo-controlled, multicenter, triple arm trial to evaluate the safety and efficacy of Cladribine Tablets in patients with early disease who had experienced a first clinical demyelinating event (FCDE) and who were at high risk of converting to CDMS, according to Poser criteria. Patients taking Cladribine Tablets (3.5 mg/kg) demonstrated statistically significant differences to the placebo group in the time to CDMS conversion during the initial treatment period up to the data cut-off (Leist, 2014).

Additionally, treatment with Cladribine Tablets significantly reduced the number of T1 Gd+-enhanced lesions, new or enlarging T2 lesions, and combined unique active MRI lesions compared with placebo (Leist, 2014). Cladribine Tablets were associated with clinical and

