8.1.1.8 Conversion to Clinically Definite Multiple Sclerosis (ORACLE MS Participants Only)

Conversion to CDMS will be determined according to the McDonald 2017 criteria (Thompson, 2018; Table 2). For more details please see Appendix 6 2017 Mc Donald Criteria (From Thompson, 2018)).

Table 2 The 2017 McDonald criteria for diagnosis of Multiple Sclerosis in patients with an attack at onset

Clinical Presentation	Additional Data Needed to Make MS Diagnosis

 • ≥ 2 attacks and objective clinical evidence of ≥ 2 lesions • ≥ 2 attacks and objective clinical evidence of 1 lesion with historical evidence of prior attack involving lesion in different location 	
None. Dissemination in space (DIS) and dissemination in time (DIT) have been met.

 • ≥ 2 attacks and objective clinical evidence of 1 lesion 	
One of these criteria:
 
 • DIS: additional clinical attack implicating different CNS site • DIS: ≥ 1 symptomatic or asymptomatic MS-typical T2 lesions in ≥ 2 areas of CNS: periventricular, juxtacortical/cortical, infratentorial or spinal cord

 • 1 attack and objective clinical evidence of ≥ 2 lesions 	
One of these criteria:
 
 • DIT: additional clinical attack • DIT: simultaneous presence of both enhancing and non-enhancing symptomatic or asymptomatic MS-typical MRI lesions • DIT: new T2 or enhancing MRI lesion compared to baseline scan (without regard to timing of baseline scan) • Cerebrospinal fluid (CSF)-specific (i.e. not in serum) oligoclonal bands

 • 1 attack and objective clinical evidence of 1 lesion 	
One of these criteria:
 
 • DIS: additional attack implicating different CNS site • DIS: ≥ 1 MS-typical symptomatic or asymptomatic T2 lesions in ≥ 2 areas of CNS: periventricular, juxtacortical/cortical, infratentorial or spinal cord 
AND
 
One of these criteria:
 
 • DIT: additional clinical attack • DIT: simultaneous presence of both enhancing and non-enhancing symptomatic or asymptomatic MS-typical MRI lesions • DIT: new T2 or enhancing MRI lesion compared to baseline scan (without regard to timing of baseline scan) • CSF-specific (i.e. not in serum) oligoclonal bands

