8.10 Health Economics

Not Applicable.

9 Statistical Considerations

One interim and 1 final analysis are planned for this study.

Study data will be integrated with study data from the parent studies as required to perform the statistical analyses.

Generally, data will be analyzed descriptively with the following measures: mean with standard deviation, median with interquartile range, minimum and maximum for continuous variables and counts with percentages for categorical variables. Missing data will also be summarized. Patients' demographic factors and clinical characteristics at enrolment will be summarized descriptively as detailed above.

As the study visits are around 10 years after the initial treatment with IMP in the parent studies, it is likely that only a specific type of participants from these trials is available for follow-up. A potential selection bias will be evaluated by comparing the characteristics of those patients randomized to the parent studies and those patients included in this study.

Methodological approaches which evaluate and address this potential selection bias will be further detailed in the Statistical Analysis Plan (SAP). Differences in study populations will be considered when making inferences based upon study results. With this in mind, analyses

will generally be exploratory and for hypothesis generating purposes. Parameter estimates with associated 95% confidence intervals (CIs) will be reported for the study endpoints, as appropriate

The analytical approach for all endpoints is described below and will be further detailed in the integrated Analysis Plan (iAP).

All procedures outlined within this section will be undertaken using a SAS statistical analysis software (version 9.4 or higher).

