Cladribine high/placebo (HLPP): Subjects who were randomized to cladribine high dose with 1 or 2 cladribine 10 mg tablets per day over 4 to 5 days in Weeks 1, 5, 9, and 13 of Year 1, followed by Weeks 1 and 5 of Year 2 of the CLARITY study (25643) (total dose 5.25 mg/kg), and then to placebo for the years 1 and 2 of the CLARITY extension.

Cladribine low/placebo (LLPP): Subjects who were randomized to cladribine low dose with 1 or 2 cladribine 10 mg tablets per day over 4 to 5 days in Week 1 and Week 5 of Years 1 and 2 of the CLARITY study (25643) (total dose 3.5 mg/kg), then on placebo for the years 1 and 2 of the CLARITY extension study.

Placebo/Cladribine low dose (PPLL): Subjects who were randomized to placebo for the first and second year of CLARITY study (25643), then to cladribine low dose with 1 or 2 cladribine 10 mg tablets per day over 4 to 5 days in Week 1 and Week 5 of Years 1 and 2 of the CLARITY extension study.

Due to administrative reasons, there was a varying period (median time 41 weeks, range 1 day to 118 weeks) between a subject completing the CLARITY study and starting in the CLARITY EXT study, subjects did not receive cladribine during this time period. Following the end of the 96-week CLARITY EXT study period, subjects were followed for safety for an additional 24 weeks. The primary objective of this trial was to evaluate the safety of extended treatment with oral cladribine when administered to subjects who completed CLARITY (25643).

ORACLE MS (28821): The ORACLE MS (ORAl CLadribine in Early MS) study was a Phase III, randomized, double-blind study to evaluate the safety and efficacy of oral cladribine tablets as a monotherapy in subjects at risk of developing MS (subjects who have experienced a first clinical event suggestive of MS). Subjects were randomized to either oral cladribine high dose with 1 or 2 cladribine 10 mg tablets per day over 4 to 5 days in Weeks 1, 5, 9, and 13 of Year 1, followed by Weeks 1 and 5 of Year 2 (total dose 5.25 mg/kg), or oral cladribine low dose with 1 or 2 cladribine 10 mg tablets per day over 4 to 5 days in Week 1 and Week 5 of Years 1 and 2 (total dose 3.5 mg/kg), or matching placebo. The design was a time-to event design with treatment schedules dependent on conversion to clinically definite multiple sclerosis (CDMS) according to the Poser criteria at any time during the first 96 weeks:

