9.5 Handling of missing data/ Presentation of continuous and qualitative variables

It is anticipated that missing/not reported data will feature many of the endpoints, especially BVMT-R and SDMT (see section 14.3.3). No imputation will be done for these assessments.

In general, missing or partial dates will be imputed as follows:

- If year and month available but day is missing, impute day to 15
- If only year available, impute day and month to 15JUN
- If date is completely missing, then no imputation will be done, except for Concomitant Medication end dates: if end date is completely missing (day, month and year) and partial or complete start date then end date will be imputed to be the last study assessment date.

In addition, for concomitant medication dates:

- If imputed start date is after end date, then the start date will be set equal to end date.
- If imputed end date is before start date, then the end date will be set equal to start date.

For time to event analyses, if partial date does not determine whether event occurred before or after start date, then analysis date will be set equal to start date, subject will be censored and time to censoring = 1/365.25.

Continuous variables:

Continuous variables will be summarized using descriptive statistics, i.e.

- number of subjects (N),
- number of subjects with non-missing values,
- number of subjects with missing values
- mean and standard deviation,

- median, 25th Percentile - 75th Percentile (Q1-Q3),
- minimum, and maximum.

Qualitative variables:

Qualitative variables will be summarized by counts and percentages.

There are no plans for any formal statistical inference. This study will adhere to the Guidelines for Good Pharmacoepidemiology Practices (GPP). Data evaluation and interpretation will be based on point estimates and 95% corresponding confidence intervals (CI). Due to the exploratory nature of the study, an adjustment for multiple comparisons is not required.

Analyses will be performed using SAS® Software version 9.4 or higher.

10 Study Participants

The subsections in this section describe the specifications for reporting participant disposition and study discontinuations.

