14.1 Primary Endpoint

The primary efficacy endpoint of this study will be evaluated descriptively by percentage and 95% CI of patients using a wheelchair most of the time ($EDSS \geq 7$) in the 3 months prior to Study Visit 1 or patients bedridden any time prior to visit 1. Forest plots will also be used to display these results.

In addition, analysis will be adjusted via logistic regression with parent studies (CLARITY or ORACLE), treatment group, and disease duration (at study visit 1) as continuous variable as factors for cohort A and with only disease duration (at study visit 1) as factors for cohort B, C and D. Estimate with likelihood based 95% CI within each parent study treatment group (exposed/not exposed) will be presented.

To identify the primary endpoint, the following source data used will be:

- Both AWB eCRF page and retro EDSS page will be considered. ($EDSS \geq 7$ in the 3 month prior to SV1 or $EDSS \geq 8$ after FDIMP)
- $EDSS \geq 7$ will also be considered (EDSS SV1).
- Participants who died due to MS are included in this proportion also (reason of death is MS disease related).

Disease duration = $(SV1 - \text{date of MS diagnosis} + 1) / 365.25$

Date of MS diagnosis is taken from CLARITY eCRF for CLARITY and CLARITY EXTENSION patients. For ORACLE MS patient, the MS diagnosis is the date of CDMS conversion collected either during the parent study or after the end of the parent study until SV1.

Logistic Regression:

The following SAS code will be used:

```
proc genmod data=sourcedata;
where avalc ne "U";
class STUDY TRT ;
model avalc = STUDY TRT DISEASE_DUR /dist=binomial link=logit lrci wald;
  Estimate "Never Exposed to Cladribine" intercept 1 Trt 1 0 / exp e;
  Estimate "Exposed to Cladribine" intercept 1 Trt 0 1 / exp e;
  Estimate "Never Exposed to Cladribine vs Exposed to Cladribine" Trt -1 1
/exp e;
  lsmeans trt / cl;
  ods output estimates=ESTIMATES lsmeans=lsmean; run;
```

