14.3.2 Durability of clinical outcomes

Durability of clinical outcomes will be summarized descriptively and evaluated via retrospective data collection from medical records or at Study Visit 1:

- Proportion of study participants being bedridden
- Time from first dose of IMP to first use of an ambulatory device
- Time from last dose of IMP to first use of an ambulatory device
- Time from first dose of IMP to first use of a wheelchair
- Time from last dose of IMP to first use of a wheelchair
- Number of MS relapses between the end of parent study to Study Visit 1
- ARR from time of first dose of IMP to SV1, and by 2-year intervals
- ARR from time of last dose of IMP to SV1, and by 2-year intervals
- % and Time to conversion to CDMS (For Cohort D participants only)
- Proportion of study participants diagnosed as Secondary Progressive MS (SPMS) without relapses in the 3 months prior to SPMS diagnosis
- Proportion of study participants diagnosed as SPMS with relapses in the 3 months prior to SPMS diagnosis
- Proportion of study participants diagnosed as Primary Progressive MS (PPMS) (For Cohort D participants only)

Computational rule:

Participants being bedridden, first use of an ambulatory device and first use of a wheelchair are collected on “ambulatory - bedridden status and first use of wheelchair” eCRF page.

Participants diagnosed as SPMS with and without relapses in the 3 months prior to SPMS diagnosis are collected on “History of MS onset” eCRF page and Participants diagnosed as PPMS are collected on “conversion to CDMS” eCRF page.

Time to first ambulatory device/wheelchair

Kaplan Meier curve and estimates including number of subjects at risk, number of subjects with an event and subject censored will be presented for time to first ambulatory and wheelchair from first and last dose of IMP administered, by treatment group (exposed vs never exposed) and overall

Computation rule:

Whichever come first will be considered as an event:

- 1) CRF Ambulatory device page, wheelchair use date
- 2) CRF Ambulatory device page, ambulatory device use date
- 3) EDSS score ≥ 6
- 4) Death due to MS

Kaplan Meier SAS code:

AVAL = time-to-event response variable

CENSOR = censoring variable (0 = event, 1 = no event)

TRT= Trt group (“Exposed to Clad” “Never exposed to Clad”)

Code:

```
PROC LIFETEST DATA=ADTTE OUTSURV=RESULTS ALPHA=0.05 METHOD= KM Conftype =  
Loglog;  
TIME AVAL*CENSOR(1);  
STRATA TRT;  
RUN;
```

Annualized Relapse Rate:

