ARR from time of FDIMP to Study Visit 1 is calculated for each treatment group:

$$\text{ARR} = [(\text{sum of relapses} * 365.25) / (\text{sum of time on study in days until SV1})]$$

ARR from time of FDIMP to Study Visit 1 and by 2-year intervals is calculated for each treatment group:

$ARR = [(sum\ of\ relapses\ *365.25) / (sum\ of\ time\ on\ main\ study\ by\ 2\text{-}year\ intervals\ in\ days\ until\ SV1)]$

Time on study = Study Visit 1 – first dose of IMP +1

ARR from time of last dose of IMP to Study Visit 1 will be calculated similarly.

Table 5: Time window for ARR by 2-year intervals

Cumulative intervals	Time intervals
Less than 2 years	1 to 730 days
2 nd years to 4 th years	731 to 1461 days
4 th years to 6 th years	1462 to 2191 days
6 th years to 8 th years	2192 to 2922 days
X th years to Y th years...	Truncate (X*365.25 +1) to truncate (Y*365.25) days

Time to CDMS (Cohort D only)

Number of participants who converted to CDMS since first and last dose administered will be summarized descriptively.

Both information collected in “Conversion to CDMS” eCRF page and ORACLE MS parent study dataset will be used to identify participants who converted to CDMS after first/last dose of IMP.

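### The adjusted primary-endpoint model drops ORACLE participants who never converted to CDMS, and its SAS code does not deliver the within-group estimates and likelihood intervals that the text promises

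*SAP*

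**What the plan says.** SAP 14.1 supplements the unadjusted percentage with a logistic model. In Cohort A the factors are parent study, treatment group and disease duration. For Cohorts B, C and D the text names disease duration alone. Duration is Study Visit 1 minus date of MS diagnosis, plus one day, in years. CLARITY participants use the diagnosis date from their eCRF. For ORACLE: "For ORACLE MS patient, the MS diagnosis is the date of CDMS conversion collected either during the parent study", or later up to Study Visit 1.

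On missing dates SAP 9.5 says: "If date is completely missing, then no imputation will be done". The one exception concerns concomitant medication end dates.

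Conversion is treated elsewhere as something that only some participants reach. SAP 14.3.2 lists a percentage "and Time to conversion to CDMS (For Cohort D participants only") and adds: "Number of participants who converted to CDMS since first and last dose administered will be summarized descriptively".

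The definition of conversion also changes. The parent study used "conversion to clinically definite multiple sclerosis (CDMS) according to the Poser criteria at any time during the first 96 weeks", whereas Protocol 8.1.1.8 says: "Conversion to CDMS will be determined according to the McDonald 2017 criteria".

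The text of 14.1 promises an estimate with a likelihood-based 95% CI within each treatment group. The code declares STUDY and TRT as CLASS variables and puts LRCI on the MODEL statement. It has two group ESTIMATE rows, one TRT contrast and LSMEANS with CL, and it saves only the ESTIMATE and LSMEANS tables.

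**The concern.** ORACLE enrolled people at a first demyelinating event, so not having converted by Study Visit 1 is an ordinary state. Under 14.1 these people have no duration. The only exclusion written in the code is for an unknown outcome, so they would leave the model without the SAP saying so. For ORACLE the adjusted proportion would then describe converters, a group defined by an event after treatment began. Among converters the covariate is itself post-treatment, with an origin that mixes two diagnostic definitions.

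This is the only adjusted analysis of the primary endpoint. Separately, a programmer who follows the code would not obtain the within-group estimates and intervals described, and could attach the wrong group name to an estimate.

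**Working it through.** The plan states no figure for this model, so there is none to reproduce. Three properties of the software are assumed, because the documents do not state them: listwise deletion, Wald limits for ESTIMATE and LSMEANS, and alphabetical CLASS ordering by default.

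**1. Who is lost.** No conversion date means no duration, no imputation (SAP 9.5) and so no place in the model. Protocol 9.4.1 allows multiple imputation, but only as an option for missing endpoint data, and SAP 14.1 does not take it up.

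Inputs: 1326 CLARITY and 617 ORACLE participants, total 1943 (SAP 6.1); recruitment scenarios of 587 to 1175 (Protocol 9.2, which starts from 1,958). The never-converted share f is not in the documents. If enrolment keeps the parent mix, the loss is f of Cohort D and f x 617/1943 = 0.3176f of Cohort A.

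| f (assumed) | Cohort D lost | Cohort A lost |
|---|---|---|
| 5% | 5% | 1.6% |
| 10% | 10% | 3.2% |
| 20% | 20% | 6.4% |
| 40% | 40% | 12.7% |

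At f = 10% the Cohort A loss is 0.10 x 0.3176 x 587 = 18.6, or about 19 people, and 0.10 x 0.3176 x 1175 = 37.3, or about 37.

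**2. Effect on the proportion.** In Cohort D, the converters' risk minus the risk in everyone is r_c - [(1 - f)r_c + f r_n] = f(r_c - r_n). It is zero if the risks are equal. With r_n = 0 and r_c at the protocol's planning values of 5% to 15% (assumptions), the upper bound at f = 10% is 0.5 to 1.5 points. In Cohort A, standardised to the parent mix, it is 0.3176 times that, or 0.16 to 0.48 points. The coded LSMEANS weight the studies equally on the logit scale. With CLARITY at the same risk as the converters, 15% in both becomes 15% and 13.5%; the mean logit is (-1.735 - 1.857)/2 = -1.796, or 14.23%, a gap of 0.77 points. At 5% the gap is 0.26 points.

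**3. Estimability.** With CLASS coding, the intercept column equals the sum of the STUDY columns and the sum of the TRT columns. In an estimable row the intercept coefficient must therefore equal the sum of the STUDY coefficients and the sum of the TRT coefficients.

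| Row, Cohort A | Intercept | STUDY sum | TRT sum | Estimable |
|---|---|---|---|---|
| `intercept 1 Trt 1 0` | 1 | 0 | 1 | no |
| `intercept 1 Trt 0 1` | 1 | 0 | 1 | no |
| `Trt -1 1` | 0 | 0 | 0 | yes |
| LSMEANS (STUDY 0.5, 0.5) | 1 | 1 | 1 | yes |

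A numerical rank check gives the same answers. If STUDY is dropped and TRT kept, as may be meant for Cohorts B-D, the two group rows become estimable and print without a flag, but at duration 0.

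**4. Labels.** If TRT level 1 is never exposed, the group labels hold and `Trt -1 1` is exposed minus never, against its label. If level 1 is exposed, the contrast label holds and the group labels are swapped. No order satisfies all three. The modelled level of `avalc` is not stated either.

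**5. Interval.** LRCI gives profile-likelihood limits for model coefficients. The within-group quantities come from ESTIMATE and LSMEANS, whose limits are Wald, with LSMEANS on the logit scale. For scale, 3 events in 60 gives 1.6% to 14.4% (Wald) against 1.3% to 12.5% (profile).

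**The case against.** Much can be said for the plan.

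- The unadjusted percentage and CI, which are the main result, do not use duration, and the study tests no hypothesis. This stands.
- The never-converted share may be small. Protocol Section 9 says: "As the study visits are around 10 years after the initial treatment with IMP in the parent studies". McDonald 2017 may also leave fewer people unconverted than Poser. This stands; the documents do not settle it.
- A reader might infer that the exclusions go unreported. SAP 11.1 summarises disease duration by treatment group and cohort, and SAP 9.5 requires a missing count for continuous variables. However, the list in 11.1 is headed as based on first dose, and nothing ties that count to the model.
- A reader might infer that no likelihood interval, or no group estimate, is produced at all. Neither is so: LRCI covers the coefficients, including TRT, and LSMEANS is estimable and saved. Only the within-group likelihood interval is missing.
- A reader might infer that a reversed treatment contrast will be published. The Kaplan-Meier code in SAP 14.3.2 names the TRT values so that the exposed group sorts first. If the same values and default ordering apply here, the contrast label is right, and in Cohort A the swapped group rows are non-estimable anyway. Swapped rows would print unflagged only in Cohorts B-D, and only if TRT is kept there.
- Groups are as-treated, and in ORACLE open-label cladribine followed McDonald conversion (SAP 6.2), so exposure already depends partly on disease course. This limits what any exposed-versus-never comparison can show, but it does not give non-converters a duration.

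**Conclusion.** The point holds for the adjusted analysis only. As written, SAP 14.1 leaves duration undefined for ORACLE participants who have not converted and so removes them from the model in Cohorts A and D. Its code does not match its text on group estimates, labels or interval. It should be fixed, but it does not threaten the unadjusted result.

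The size rests on assumptions about f, the enrolment mix and the risk in non-converters. Per 10% never converted, the bias lies between zero and the bounds in the check, provided that non-converters are at no higher risk than converters. For Cohort A even the equal-weight bound of 0.77 points is just under the smallest half-width in Protocol 9.2 (0.79 points).

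A stronger reading is tempting: that cladribine changes who converts, so the loss differs by treatment group and distorts the comparison. Protocol 2.2 reports "statistically significant differences to the placebo group in the time to CDMS conversion during the initial treatment period up to the data cut-off". That concerns timing within the parent trial. A difference between groups in who has converted by Study Visit 1 is plausible, but the documents do not show it.

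**What to change.** 1. **Duration origin.** For ORACLE, start at a date that every participant has: first dose of IMP, already defined in SAP 9.3, or the first clinical demyelinating event if the parent-study data hold that date. The documents make that event an eligibility condition but do not show that its date is available. State that the covariate then differs in meaning from CLARITY's. STUDY shifts only the intercept, so a common slope is an assumption; a STUDY by duration term can check it.
2. **End date and exclusions.** State the end date for participants without a Study Visit 1 date, such as MS deaths counted as events. Report the number excluded from the model by treatment group.
3. **Group estimates.** Replace the group ESTIMATE rows with LS-means on the inverse-link scale, or with rows that give explicit STUDY weights and mean duration. The weights matter: with CLARITY at 15% and ORACLE at 5% (assumed), equal weights give 8.8% and the parent mix of 68.2:31.8 gives 10.7%.
4. **Interval.** Refit without an intercept, as logit p = t_TRT + b(STUDY - w) + g(duration - mean), where w is the chosen study weight. The TRT parameters are then the group logits and LRCI gives their profile limits. Otherwise change the text to Wald.
5. **Labels and models.** Fix the TRT order and the modelled level of `avalc`, make each label match its coefficients, and state whether TRT is in the Cohort B-D models.

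The cost is some SAP wording and a few lines of code. Using first dose needs no new data.
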